12.7.4 Radiologic Evaluations

Patients with newly diagnosed GBM will be imaged by MRI as per standard of care for eligibility and baseline measurements, and to assess progression prior to vaccine therapy; although the purpose of this study is not to detect tumor responses, any evidence of tumor response will be determined according to the Duke PRTBTC standard operating procedure (SOP). Immunotherapy Response Assessment in Neuro-Oncology (iRANO) criteria [122, 123] established by consensus conference, will be used for assessment of response and pseudoprogression following immunotherapy. If pseudoprogression is suspected, the subject will continue with vaccine therapy for a minimum of 2-3 subsequent months so long as subject remains clinically and radiographically stable compared to the MRI showing suspected pseudoprogression. If the subject continues to do well beyond the 3 months, they will continue on study as planned. Subjects demonstrating definitive progression will be removed from study. Tumor progression will need to be documented histologically, unless there are clinical contraindications, to exclude inflammatory responses presenting as radiographic or clinical changes, which could indicate potentially toxic or therapeutic responses and not tumor progression. If tissue is obtained through the Duke Brain Tumor Biorepository, it will be used to confirm tumor progression histologically and to assess immunologic cell infiltration and examine pp65 expression to evaluate antigen loss at the tumor

site. Upon progression, patients may be treated on other therapies as directed by the treating Oncologist.

12.7.5 Immunologic Assessments

Immunological response evaluations will be conducted as described in [Table 4](#). All patients will undergo at least 2 leukapheresis procedures – prior to radiation (1 red top 10mL tube) and approximately 2 weeks post vaccine #3 (9 yellow ACD 8.5mL tubes, 2 red top 10mL tubes). If an additional leukapheresis must occur earlier than 14 (\pm 4) days after vaccine 3, then no immune monitoring will be drawn at this additional leukapheresis. For subjects who complete all 10 study vaccines without progressing, an attempt will be made to obtain blood for immunologic monitoring 2-3 times a year at standard Duke neuro-oncology visits and at progression (whichever comes first). The immune monitoring blood that is collected prior to the initiation of post RT-TMZ cycle 1 (on the same day) will be the baseline for T_{reg} analysis. The immune monitoring blood drawn at pre-vaccine #1 will be the baseline for polyfunctional T cell analysis. The blood drawn on the same day as (but prior to) Td preconditioning will be analyzed for the baseline CCL3. A comparison of pre-therapy lymphocyte functions to those at intervals after each immunization will be made. These tests may provide evidence for the development of immune responses following DCs immunization and will play an important role in the design of future DC-based clinical trials. Cellular immune responses to pp65 will be measured by polyfunctional T cell assays using 10-12 color panels previously optimized in our laboratory, which includes detection of CCL3 on T cells. The effect of treatment on cytokines and other soluble factors will be assayed in the serum/plasma. Serum/plasma will be measured to determine levels of CCL3 from the blood drawn at the Td preconditioning visit, and at the vaccine #4 visit. T_{Reg} kinetics will be measured by using a constellation of markers specific for T_{Reg} s such as foxp3, CD25 and CD4. Whenever blood for immune monitoring is obtained, we will submit a CBC with auto differential to assess absolute number of T_{Reg} s. These will be drawn with SOC blood draws whenever possible.

In addition, blood and tumor samples will be stored for possible future research in the Duke BTIP Laboratory where all other samples from this study are stored. The samples being stored are ONLY for this study. Our mouse studies being done in the BTIP Lab are identifying markers that may influence migration, therefore, as other markers are identified, we would like to investigate whether these same markers are identified in human subjects enrolled on this trial.

Polyfunctional Flow Cytometry

Peripheral blood will be drawn into 9 yellow (ACD) tubes containing acid citrate dextrose and 2 red top tubes for serum. PBMCs will be separated by density gradient centrifugation using Leukosep tubes.

Polyfunctional T cell analysis will be done in [name] immunology laboratory. [name] immunology laboratory conducts all the clinical immune monitoring for the Duke Brain Tumor Center. Polyfunctional T cell panels have been developed in our laboratory and optimized for detection of CCL3 in T cells. This process involves the rapid early detection and analysis of the production of Tumor Necrosis Factor- α (TNF- α), CCL3, IFN- γ , interleukin-2 (IL-2), and CD107a (a marker of cell cytotoxicity) prior to cellular secretion following antigen-specific stimulation *in vitro*. The functional CD4 and CD8 immune response of the patients will be monitored using a 10-12-color assay. To detect an increase in polyfunctional T cells we will analyze the fold change of T cells secreting TNF- α , CCL3, IFN- γ , IL-2 and CD107a from the blood

samples from pre-vaccine 1, and second leukapheresis (or blood draw) occurring $14 \pm (4)$ days after vaccine #3.

Isolated PBMCs will be stimulated for 6 hours with the pool of 138 peptides spanning the entire pp65 gene. The cells will be stained for the surface markers CD3 (to identify it as a T cell), CD4 (to define as specific helper cell), CD8 (to define antigen specific cytotoxic T cells) and then submitted for intracellular cytokine staining. This procedure allows for the highly sensitive detection of TNF- α , CCL3, IFN- γ , IL-2 and CD107a secreting cells, which are assumed to be specifically responding to the stimulating antigen.

The maturation state and the activation status of samples will be detected by polychromatic flow cytometry using optimized panels which will include CD3, CD4, CD8, CCR7, CD45RA, HLA-DR, CD69 and HLA-DR. Levels of naïve (TN – CD45RA+CCR7+), central memory (TCM – CD45RA-CCR7+), effector memory (TEM – CD45RA-CCR7-), or terminally differentiated effector memory (TEMRA – CD45RA+CCR7+) T cells .

Serology/Multiplex Platform

CCL3 and levels of other inflammatory soluble factors may be assayed by multiplex platform. The effect of treatment on CCL3 Serum/plasma will be assayed (2 red top 10 mL tubes) to determine if levels of CCL3 are impacted by Td pre-conditioning and will be drawn prior to the Td pre-conditioning as described above, and at the vaccine #4 visit (9 yellow ACD 8.5 mL tubes, , 2 red top 10 mL tubes) 24 hours after Td pre-conditioning. Antibody levels to the immunizing antigen may be measured.

T_{Reg} Kinetics

T_{Reg}s will be analyzed by flow cytometry using a constellation of markers specific for T_{Reg}s included CD4, CD25 and foxp3. For T_{Reg} analysis, the time points will be leukapheresis 1, before DI TMZ in the Post-RT TMZ, pre-vaccine 1, leukapheresis 2, pre-vaccine 4, pre-vaccine 5, & pre-vaccine 6. We will analyze the percent of Foxp3, CD25, CD4 T cells over these time points.

13 SAFETY MONITORING AND REPORTING

13.1 Adverse Events

An AE is any untoward medical occurrence in a subject receiving pre-conditioning or the study vaccine and which does not necessarily have a causal relationship with this treatment. For this protocol, the definition of AE also includes worsening of any pre-existing medical condition. An AE can therefore be any unfavorable and unintended or worsening sign (including an abnormal laboratory finding), symptom, or disease temporally associated with the use of the DCs, whether or not related to use of the DCs. Abnormal laboratory findings without clinical significance (based on the PI's judgment) should not be recorded as AEs. But, laboratory value changes that require therapy or adjustment in prior therapy are considered adverse events.

Adverse events will be collected from the time of administration of the first DC vaccine through 1 month after the subject's last vaccine, all AEs must be recorded in the subject's medical record and adverse events case report form.

AEs will be assessed according to the CTCAE version 5. If CTCAE grading does not exist for an AE, the severity of the AE will be graded as mild (1), moderate (2), severe (3), life-threatening (4), or fatal (5).

Attribution of AEs will be indicated as follows:

- Definite: The AE is clearly related to the study drug
- Probably: The AE is likely related to the study drug
- Possible: The AE may be related to the study drug
- Unlikely: The AE is doubtfully related to the study drug
- Unrelated: The AE is clearly NOT related to the study drug

Attribution of AEs will be determined for each study intervention individually (pp65 DC vaccine, pre-conditioning agent [Td], TMZ, bevacizumab).

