12.4 Follow-up Period

Patients will be followed for survival, progression, and subsequent therapies only, and this data will be recorded by the research team. For recording of subsequent therapies, the type of therapy(ies) that the subject receives will be recorded with approximate start and stop date, if possible. For subjects who complete all 10 study vaccines without progressing, an attempt will be made to obtain blood for immunologic monitoring 2-3 times a year at standard Duke Preston Robert Tisch Brain Tumor Center visits. If the subject progresses in the follow-up period, blood for immunological monitoring will be drawn at the time of progression, if possible.

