12.5 End of Study

Rationale for taking a patient off study will be documented (see Section [12.6.1](#)). In the Follow-up Period, patients will be followed for survival, progression, and subsequent therapies only, and this data will be recorded by the research team.

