Monitoring Plan	
Table A: Toxicity Monitoring Rules
 
  
 Number of patients accrued	Number of patients with unacceptable toxicity requiring accrual suspension	
   
 ≤ 5	≥ 2	
 
 6-11	≥ 3	
 
 12-17	≥ 4	
 
 18-23	≥ 5	
 
 24-29	≥ 6	
 
 30-34	≥ 7	
 
 35-39	≥ 8	
 
 ≥ 40	≥ 9	
  
 
Given that both long- and short-term toxicities are of interest in this study, it is not feasible to suspend accrual while toxicity is assessed as is often done in phase I trials. If the criteria in Table A are satisfied or there are other reasons for concern about the safety of patient treatment (e.g., treatment-related toxic death), accrual will be suspended and data will be carefully reviewed to determine if accrual should be permanently terminated or the protocol modified. Table A provides conditions under which accrual will be temporarily suspended and data carefully reviewed to determine the appropriate action, including permanent study termination, continuation with patient accrual after appropriate amendment, or continuation with patient accrual with no modification of the protocol. These guidelines have not been adjusted for differential length of follow-up of accrued patients.
 
If a death occurs within 30 days of DC vaccine administration, that is not attributable to progressive disease or other obvious non-study related cause (i.e. motor vehicle accident), enrollment of new subjects and all vaccinations will be suspended until review by the PI and IND sponsor has been completed and the FDA notified. If attribution of death is determined by the PI, IND sponsor or FDA to be possibly, probably, or definitely related to trial drug, then continued treatment of all enrolled subjects with trial drug will be suspended until the review is completed and recommendations for the study continuation have been
	Number of patients accrued	Number of patients with unacceptable toxicity requiring accrual suspension	≤ 5	≥ 2	6-11	≥ 3	12-17	≥ 4	18-23	≥ 5	24-29	≥ 6	30-34	≥ 7	35-39	≥ 8	≥ 40	≥ 9
Number of patients accrued	Number of patients with unacceptable toxicity requiring accrual suspension																		
≤ 5	≥ 2																		
6-11	≥ 3																		
12-17	≥ 4																		

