18-23	≥ 5																		
24-29	≥ 6																		
30-34	≥ 7																		
35-39	≥ 8																		
≥ 40	≥ 9																		

	
issued and approved by FDA. Any death attributed to trial drug, regardless of the timeline with respect to last treatment, will result in suspension of enrollment and suspension of continued treatment for enrolled subjects until review by FDA is complete and recommendations for study continuation issued and approved.

TABLE B: Probability of Accrual Suspension	
Underlying unacceptable toxicity Rate	Probability of accrual suspension
0.05	0.036
0.10	0.200
0.15	0.502
0.20	0.784
0.25	0.936
0.30	0.987

	The probability of accrual suspension as a function of the true unacceptable toxicity rate is provided in Table B. These statistics were generated assuming toxicity outcome was known at the time of accrual, and ignored issues such as time to toxicity, accrual rate, and length of follow-up. Every 6 months from the time the first patient received vaccine #1, the toxicity experienced by patients accrued to this study will be summarized and reviewed regardless of the number of patients accrued to determine whether the overall toxicity profile of treatment is unacceptable or not.
Analysis Plan	The proportion of patients who experience an unacceptable toxicity as defined in Section [9.1.1](#)
Additional Analyses	Adverse events will be summarized in several other forms to satisfy scientific and monitoring needs, as well as various regulatory reporting needs (e.g. FDA, DCI Safety Oversight Committee, and ClinicalTrials.gov). For these summaries, the frequency of adverse events will be tabulated by the maximum grade experienced.

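### Late toxicity and late drug-attributed deaths matter to Section 15.6.5, but adverse event collection ends 1 month after the last vaccine and follow-up names no reliable way to record them

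*Combined protocol and SAP*

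**What the plan says.** Four parts of the combined protocol and SAP bear on this.

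- **Section 15.6.5, Monitoring Plan.** The reason given for not pausing accrual while toxicity is assessed begins "Given that both long- and short-term toxicities are of interest in this study". The text on deaths ends with a rule that has no time limit: "Any death attributed to trial drug, regardless of the timeline with respect to last treatment, will result in suspension of enrollment". Continued treatment is suspended as well, until FDA review is complete.
- **Section 13.1.** Adverse events are collected "from the time of administration of the first DC vaccine through 1 month after" the last vaccine.
- **Section 12.4.** "Patients will be followed for survival, progression, and subsequent therapies only, and this data will be recorded by the research team". Section 12.5 repeats the restriction: "In the Follow-up Period, patients will be followed for survival, progression, and subsequent therapies only".
- **Section 12.6.2.** Everyone who starts DI-TMZ is followed until death or loss to follow-up.

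The objective #5 endpoint is the proportion of DI-TMZ starters with unacceptable toxicity as defined in Section 9.1.1. That definition covers Grade 3 autoimmune toxicity requiring steroids or hormone replacement, and it sets no limit on time of onset.

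**The concern.** The safety objective and the death rule look beyond the end of vaccination, while the data collection sections largely stop there. A site that follows Sections 12.4 and 13.1 literally would not record a Grade 3 autoimmune event arising some months after the last vaccine, even though it meets Section 9.1.1. It would record the date of a late death but is not told to record its cause or attribution, and attribution is what triggers the rule.

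The denominator is every DI-TMZ starter, so a patient who stops after one or two vaccines is observed for about a month after the last one and then counts as free of unacceptable toxicity. Any late event missed lowers the objective #5 proportion and, while accrual is open, the Table A count. Nothing works in the other direction. This point concerns the end of collection, not its start.

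**Working it through.** **1. The plan's own figure: Table B.** I applied the Table A limits after each patient by exact binomial recursion, with 48 patients (the DI-TMZ target in Section 15.9).

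| True rate | Table B | Recomputed |
|---|---|---|
| 0.05 | 0.036 | 0.036 |
| 0.10 | 0.200 | 0.198 |
| 0.15 | 0.502 | 0.496 |
| 0.20 | 0.784 | 0.779 |
| 0.25 | 0.936 | 0.933 |
| 0.30 | 0.987 | 0.986 |

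Table B reproduces. It describes toxicity that is actually recorded.

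**2. When the window closes** (schedule in Section 9.1 and Table 4; 30.44 days per month).

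- Vaccine 1 on day 23 is 22 days after DI-TMZ start.
- Vaccine 1 to vaccine 10: 14 + 14 + 14 + 21 + 6 × 35 = 273 days.
- Close of window: 22 + 273 + 30 = 325 days, or 325 / 30.44 = 10.7 months after DI-TMZ start.
- Shortest intervals between visits: 22 + 216 + 30 = 268 days (8.8 months). Longest: 22 + 330 + 30 = 382 days (about 12.6 months). Held or rescheduled doses could extend this.
- A patient who stops after vaccine 1: 22 + 30 = 52 days (1.7 months).

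Section 15.9 assumes 28 months of follow-up after the last patient starts. A surviving full completer then has at least 28 − 10.7 = 17.3 months without planned adverse event collection. A survivor who stopped after vaccine 1 has at least 28 − 1.7 = 26.3 months.

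**3. Share of all-cause deaths after the window.** Inputs from Section 15.9: median OS 24 months, 24 months of accrual and 28 months of further follow-up, so 28 to 52 months per patient. My assumptions are exponential survival and uniform entry.

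- λ = ln 2 / 24 = 0.02888 per month.
- P(death by analysis) = 1 − [2^(−28/24) − 2^(−52/24)] / (24λ) = 1 − (0.4454 − 0.2227) / 0.6931 = 0.679. For 48 patients this is 32.6 deaths; the plan says 33.
- P(death by 10.7 months) = 1 − 2^(−10.7/24) = 0.266.
- Share after the window = (0.679 − 0.266) / 0.679 = 61%, or about 20 of 33 deaths. With the window closing at 12.6 or 8.8 months the share is 55% or 67%.

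This supposes that nobody stops vaccination early. Early stopping raises the share.

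**4. Does it matter while the rules can still act?** If the 24 months of accrual is read as the span of DI-TMZ starts, the first patients leave adverse event collection about 24 − 10.7 = 13.3 months before accrual ends. So it can matter for Table A, though only for part of the uncovered time.

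**5. Illustration of the effect on suspension.** The documents give no late-toxicity rate, so the missed share here is purely an assumption. It means the share of unacceptable toxicities that Table A would otherwise have counted. With 48 patients:

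| True rate | 0% missed | 10% | 25% | 50% |
|---|---|---|---|---|
| 0.20 | 0.779 | 0.679 | 0.496 | 0.198 |
| 0.25 | 0.933 | 0.873 | 0.719 | 0.337 |

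**The case against.** The strongest reply is that late events do have ways in. Section 13.3.1 requires SAE reporting and states no end date. Section 9.1.3 keeps a summary of all adverse events after RT/TMZ, also without an end date. Table 4 marks adverse events at progression, which can come after the window. Section 12.6.2 follows patients to death, and Section 15.6.5 names the PI, IND sponsor or FDA as judges of attribution. All of this stands. A reader might infer that late events have no route at all, or that the late-death rule cannot operate, and the documents do not support either reading. They do leave the passages unreconciled. Section 13.3 defines an SAE as a kind of AE, so the Section 13.1 window arguably limits it. The progression mark is a single visit. A non-serious Grade 3 autoimmune event fits none of the serious-event wording. The judges of attribution are named, but the data they would use are not.

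It can also be said that long-term is undefined and might mean the ten-month vaccine course. That is fair for that sentence alone, but the death rule expressly reaches past last treatment. The plan also discloses that Tables A and B ignore time to toxicity and differential follow-up. That explains how they were calculated, not why events would go unrecorded.

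Two further limits are accepted. Part of the uncovered time falls after accrual closes, when Table A can suspend nothing. Patients who progress may receive other therapies, which makes attribution harder. The DSMB charter and the separate data and safety monitoring plan, which are not included here, may also cover some of this.

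**Conclusion.** The concern holds in a limited form: the documents contain no specified, reliable route for a late related event meeting Section 9.1.1, or for the cause and attribution of a late death. To the extent that such events go unrecorded, the objective #5 proportion can only be understated, and so can the Table A count while accrual is open.

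The window closes about 10.7 months after DI-TMZ start on schedule (8.8 to 12.6 with visit windows). The 61% figure rests on exponential survival with a 24-month median, uniform entry and no early stopping. A reader might take it as the share of toxicities missed. It is not: it counts deaths from any cause, and the size of the undercount cannot be derived from the documents. Nor is Table B miscalculated, and the death rule is a suspension pending review rather than automatic termination. A one-month window for general adverse events is a legitimate design choice. The fault is that it does not match what Section 15.6.5 asks of the data.

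**What to change.** Reconcile Sections 9.1.3, 12.4, 12.5, 13.1, 13.3.1 and 15.6.5. At the survival contacts already made under Section 12.6.2, record until death or loss to follow-up:

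- (a) any event meeting Section 9.1.1 that is judged at least possibly related to the vaccine or Td; and
- (b) cause of death, with attribution.

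Count these in the objective #5 proportion, and in Table A while accrual is open. General adverse event collection can still end at 1 month, and no treatment rule changes.

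If the sponsor prefers not to collect these items, restate the safety objective as limited to the adverse event window and name the data source on which the late-death rule relies.

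The cost is a wording amendment, a short follow-up form and a little data entry. The reported toxicity rate may come out slightly less favourable.

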13.1.1 Reporting of AEs

A summary of all adverse events (not just those considered related to the study drug) will be kept which will categorize the event by organ system, relationship to which treatment, its grade of severity, and resolution. Periodic review by the PI and monthly review at the PRTBTC Adverse Event meeting of the collective adverse events will occur with the intention of identifying any trends or patterns in toxicity. If any such trends are identified, depending on their severity and frequency, a protocol amendment will be considered.

13.2 Adverse Events of Special Interest

Adverse events will not be collected until the patient has received the DC vaccine, unless they are considered an Adverse Event of Special Interest related to the leukapheresis procedure. Only these special interest adverse events will be collected prior to the DC vaccine, all other events occurring prior to DC vaccine administration will not be recorded or monitored.

Special Interest Adverse Events that may occur during the leukapheresis procedure include:

- Allergic Reaction
- Anaphylaxis
- Pre-syncope
- Syncope
- Vasovagal reaction

Special Interest Adverse Events that may occur after the procedure, but may still be related to leukapheresis include:

- Vascular Access Complications
- Venous Injury

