All enrolled patients will undergo a leukapheresis after resection for harvest of peripheral blood lymphocytes (PBLs) for generation of DCs. Patients will then receive approximately 6 weeks of standard of care radiation therapy (RT) and concurrent TMZ at a standard targeted dose of 75 mg/m²/d (please see Package Insert uploaded in electronic IRB for standard therapy). Patients should start RT within approximately 7 weeks of surgery. [PI discretion can be used in this situation to allow patients outside of this window to enroll.] Patients who either experience progressive disease during radiation, are dependent on steroid supplements above 2 mg/day at time of first vaccination, are unable to tolerate TMZ, or whose DCs fail to meet release criteria will be withdrawn from the study and replaced. For patients whose initial leukapheresis yields less than 3 vaccines, repeat leukapheresis may be obtained a minimum of 2 weeks from the previous leukapheresis (and may be repeated as needed) if pre-apheresis blood work is within the Apheresis Center's parameters and as long as this does not cause a significant delay in treatment for the patient. At the post-RT clinic visit the patient's MRI and blood work is evaluated before starting a single post-RT cycle of dose intensified TMZ (100 mg/m²/day for 21 days). On day 23 (\pm 2 days) of the cycle, patients will receive the first of 3 pp65 DC vaccines. DC vaccines #1-3 will be given every two weeks (\pm 2 days). All patients will receive up to a total of 10 DC vaccines, with vaccines administered every 35 days (\pm 7 days) after the third vaccine, given bilaterally at the groin site unless progression occurs with no further cycles of TMZ. DC vaccines will be given intradermally (i.d.) and divided equally to both inguinal regions. Before the first DC vaccination, patients will receive 0.5 mL of Td (tetanus and diphtheria toxoids adsorbed) intramuscularly into the deltoid muscle to ensure adequate immunity to the tetanus antigen. The Td vaccine will be obtained through Duke Investigational Chemotherapy Services (ICS) Pharmacy. Patients will undergo leukapheresis again for immunologic monitoring with specific assessment of baseline antigen-specific cellular and humoral immune responses if needed for further DC generations 14 (\pm 4) days after vaccine #3. Prior to pp65 DC vaccination #4, (3 \pm 1) weeks after leukapheresis 2 the vaccine site will receive a pre-conditioning intradermal injection of Td (1 flocculation unit (Lf), in 0.3 mL of saline for a total of 0.4 mL).

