An “Adverse Event” will be defined as any adverse change from the subject’s pre-treatment baseline condition (which is assessed at the post-RT/TMZ clinic visit), including any clinical or laboratory test abnormality that occurs during the course of research. Adverse events will be categorized and graded in accordance with the NCI CTCAE (Version 5).

A “Serious Adverse Event” will be defined as an undesirable sign, symptom or medical condition which: 1) is fatal or life threatening; 2) requires inpatient hospitalization for > 24 hours or a prolongation of existing hospitalization; 3) results in persistent or significant disability/incapacity; 4) constitutes a congenital anomaly or a birth defect and/or; 5) medically significant such that it may jeopardize the subject, and may require medical or surgical intervention to prevent one of the outcomes listed above.

A summary of all adverse events (not just those considered related to study drug) that occur following RT/TMZ will be kept which will categorize the event by organ system, relationship to treatment, its grade of severity, and resolution. Periodic review by the primary investigator (PI) and weekly review at the Duke Preston Robert Tisch Brain Tumor Center (PRTBTC) Adverse Event (AE) meeting of the collective adverse events will occur with the intention of identifying any trends or patterns in toxicity. If any such trends are identified, depending on their severity and frequency, a protocol amendment will be considered.

All adverse events which are serious and unexpected should be reported immediately to [name] M.D. at [contact] during regular business hours or at [name] after hours and to the Federal Drug Administration (FDA). Fatal or life-threatening, unexpected adverse events will be reported to the FDA by telephone, facsimile, or in writing as soon as possible, but no later than 7 calendar days after first knowledge by the sponsor followed by as complete a report as possible within 8 additional calendar days. Serious, unexpected adverse events that are not fatal or life-threatening will be reported to the FDA by telephone, facsimile, or in writing as soon as possible, but no later than 15 calendar days after first knowledge by the sponsor.

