9.4 Definition of Evaluable Subjects, On Study, and End of Study

Subjects evaluable for the analysis of the primary endpoint of overall survival will include all patients who initiate DI-TMZ.

Once the patient signs an informed consent form (ICF), that subject will be considered “on study.” Rationale for taking patient off protocol treatment will be documented.

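### Adverse event collection has three conflicting start points; under Sections 13.1 and 13.2 nearly all DI-TMZ dosing precedes collection, although objective #5 covers DI-TMZ safety in all starters

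*Combined protocol and SAP*

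**What the plan says.** Three places set a start for AE collection.

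- Section 13.1: "Adverse events will be collected from the time of administration of the first DC vaccine through 1 month after" the last vaccine. Section 13.2 repeats this, excepts only leukapheresis events of special interest, and adds that "all other events occurring prior to DC vaccine administration will not be recorded or monitored".
- Section 9.1.3 defines an AE as a change from a baseline assessed at the post-RT/TMZ clinic visit, and states: "A summary of all adverse events (not just those considered related to study drug) that occur following RT/TMZ will be kept".
- Table 4 (Schedule of Events) has a combined row for concomitant medications and AEs. As the table reads in the extracted text, that row is marked from the main consent column onward, including the DI-TMZ column.

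On timing, Section 9.1 places the post-RT visit before "starting a single post-RT cycle of dose intensified TMZ", which lasts 21 days. On day 23 (± 2 days) of that cycle, "patients will receive the first of 3 pp65 DC vaccines".

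On scope, objective #5 (Table 1 and Section 15.6.5) is the safety of DI-TMZ followed by DC vaccination, and its analysis set is every patient who starts DI-TMZ. Section 15.2 puts the same patients in the toxicity summaries. Section 13.1 also says: "Attribution of AEs will be determined for each study intervention individually (pp65 DC vaccine, pre-conditioning agent [Td], TMZ, bevacizumab".

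**The concern.** The most restrictive rule does not fit the objective. A safety objective that names DI-TMZ, analysed in everyone who starts it and with attribution to TMZ required, needs AE data from the DI-TMZ period. Sections 13.1 and 13.2 exclude almost all of that period; Section 9.1.3 and Table 4 include it. No passage gives an order of precedence, so staff working from different sections would collect different data.

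At stake are the toxicity summaries (15.2) and the AE tabulations by maximum grade (15.6.5). If the restrictive rule is followed, these would make the regimen look cleaner than it is. They would omit events that arise and resolve during DI-TMZ, and would hold little or nothing for starters who stop before vaccine 1. Events not recorded at the time may not be fully recoverable later.

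**Working it through.** **1. The plan's own figures.** The plan gives no figure for uncollected time or events. Its only figures for objective #5 are the accrual-suspension probabilities in Table B. To reproduce them, apply the Table A limits b(n) after each patient, with outcome known at accrual: P_n(k) = (1 − p)·P_{n−1}(k) + p·P_{n−1}(k − 1) for k < b(n), and count any mass at k ≥ b(n) as suspended.

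| True rate p | 0.05 | 0.10 | 0.15 | 0.20 | 0.25 | 0.30 |
|---|---|---|---|---|---|---|
| Table B | 0.036 | 0.200 | 0.502 | 0.784 | 0.936 | 0.987 |
| Recomputed, N = 48 | 0.036 | 0.198 | 0.496 | 0.779 | 0.933 | 0.986 |
| Recomputed, N = 40 | 0.036 | 0.190 | 0.459 | 0.725 | 0.894 | 0.969 |

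The largest gap at N = 48 is 0.006. Table B therefore fits a denominator of 48, the planned number of DI-TMZ starters (15.9), and is not in dispute. The N = 40 row matters only for the alternative fix.

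**2. Dosing days before collection under 13.1 and 13.2.** Dosing runs on days 1 to 21. Vaccine 1 falls on day 23 ± 2, that is, days 21 to 25. Count the dosing days strictly before the vaccine day:

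- vaccine 1 on day 21: 20 of 21 (20/21 = 95.2%);
- vaccine 1 on day 22, 23, 24 or 25: 21 of 21.

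At the nominal day 23, the whole course precedes collection.

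**3. Starters who are never vaccinated.** Section 9.1 withdraws and replaces patients who, among other reasons, "are dependent on steroid supplements above 2 mg/day at time of first vaccination, are unable to tolerate TMZ". The steroid criterion is applied at the first vaccination, which comes after DI-TMZ, so a starter can be withdrawn without receiving a vaccine. Such a patient stays in the objective #5 analysis set. Under 13.1 and 13.2 the patient has no routine AE record other than leukapheresis events. Section 9.4 does not fill the gap: "Rationale for taking patient off protocol treatment will be documented" gives a reason for stopping, not a graded event. Nor does later follow-up: withdrawn starters are followed (12.6.2), but Section 12.4 limits follow-up to survival, progression and later treatments. The documents do not give the number of such patients.

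**4. Which outputs are affected.**

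- Toxicity summaries and maximum-grade tables: directly, since they cover all starters and are not restricted by attribution.
- The unacceptable-toxicity proportion (9.1.1): its first limb counts only events attributed to Td or the vaccine, so most DI-TMZ toxicity would not count even if recorded. Only the hypersensitivity/autoimmune limb and the life-threatening limb could be reached, depending on how they are read. For scale, with 48 starters one missed qualifying event is 1/48 = 2.1 percentage points. The documents give no basis for an expected number.

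**The case against.** The strongest reply is that the stated endpoint of objective #5 is the 9.1.1 proportion, and that this is barely touched. That largely stands. A reader might infer that the restrictive rule biases the proportion, or undermines the Table A monitoring, because DI-TMZ toxicity goes uncounted. The documents do not support this:

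- The first limb excludes events attributed to TMZ alone.
- The life-threatening limb depends on whether TMZ counts as a concomitant medication. The list in 13.1 does not settle that, since it also names bevacizumab, which the study does not supply (9.1.3).
- A reaction to the Td booster given before vaccine 1 counts under the first limb only if the booster is a pre-conditioning agent. Section 10.2 labels the two uses of Td separately.

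A reader might also infer that serious events during DI-TMZ would be lost. Section 13.3.1 calls for immediate reporting of all SAEs without a vaccine-based start, and Section 12.7.1 includes AEs among the history items reviewed at each visit. These routes may capture serious events. They are not secure: 13.2 conflicts with them, and 13.1 defines an AE in terms of patients receiving pre-conditioning or the vaccine. Nor would all DI-TMZ toxicity be lost, because toxicity still present at vaccine 1 can be graded then and attributed to TMZ.

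Two further inferences go too far. First, the TMZ-intolerance criterion in 9.1 need not describe DI-TMZ starters. It comes before DI-TMZ is introduced in that section and may refer to the concurrent RT/TMZ phase. Only the steroid criterion clearly yields a never-vaccinated starter. Second, subtracting the 40 patients anticipated at vaccine 4 (15.6.2) from 48 starters does not bound the number never vaccinated. Forty is a planning figure, and the difference of 8 would include losses between vaccines 1 and 4. Section 15.9 mentions 12 patients who initiate vaccine treatment, but that sentence is too unclear to use.

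None of this removes the contradiction or its effect on the descriptive safety tables.

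**Conclusion.** The point holds as a contradiction over when AE collection starts: the first DC vaccine (13.1, 13.2), after RT/TMZ with baseline at the post-RT/TMZ visit (9.1.3), and main consent (Table 4, subject to a check of its layout against the original). If 13.1 and 13.2 are followed, 20 or 21 of the 21 DI-TMZ dosing days precede collection. This count rests on the 21-day course and the day 23 ± 2 window; it measures exposure time, not lost events.

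The direct consequence is incomplete toxicity summaries and maximum-grade tables for a secondary objective. They would lack transient DI-TMZ events and, for never-vaccinated starters, non-serious events. The number of those starters is unknown. The effect on the 9.1.1 proportion is probably small and cannot be computed. The primary endpoint is not affected. The change should be made because the rule as written gives an incomplete answer to a stated objective and is cheap to correct.

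**What to change.** Reconcile Sections 9.1.3, 13.1, 13.2 and Table 4 on a single start no later than the first DI-TMZ dose, with baseline at the post-RT/TMZ visit as 9.1.3 already has it. Remove the 13.2 exclusion for the DI-TMZ period. In 15.6.5, tabulate DI-TMZ-period AEs in all starters, and add an AE check for those who never reach vaccine 1.

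The cost is a protocol amendment, about three weeks of extra AE entry per patient, and one contact for each never-vaccinated starter, because Table 4 has no visit between the DI-TMZ visit and vaccine 1.

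The alternative is to narrow objective #5 to vaccine and Td safety in vaccinated patients. That is more than a wording change. Table 1, 15.2 and 15.6.5 would need restating, and Table B would need recalculating for the smaller denominator. With N = 40 as an illustration only, the suspension probability is 0.459 at a 15% true rate and 0.725 at 20%, against 0.496 and 0.779 recomputed at N = 48. The trial would also give up its safety conclusion on the DI-TMZ part of the regimen.
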